3.3. Sample Size and Power Considerations

Based on experience with early HD participants in the prior Phase 2 PRIDE-HD study, we expect the difference in mean change from Baseline to Week 65 between the 45 mg bid treated and placebo groups to be 0.7 points on the UHDRS-TFC with a standard deviation (SD) of 1.9 points.

A total sample size of 372 participants will provide 94% power to detect a between-group difference of 0.7 points in the mean change from Baseline to 65 weeks in the UHDRS-TFC score, with an SD of 1.9 points, using a two-tailed t-test at a significance level of 0.05. Assuming a drop-out rate of 22.5%, a total of 480 participants will be randomized. The sample size was calculated using SAS version 9.4 PROC POWER.

Based on feedback from Regulatory Authorities, the power assessment was updated as below. Assuming a dropout rate of 22.5 % in each treatment group early in the study, under assumption of Missing Not at Random (MNAR) with imputed values for all discontinued participants estimated based on the trajectory of placebo participants with available data, we anticipate a difference in change from Baseline to imputed values at Week 65 for this group to be 0.1 points. The overall difference would then be 0.565 (0.7*0.775+0.1*0.225) or 0.7 points for the 77.5% completers and 0.1 points for the 22.5 % participants who discontinue and have imputed data at Week 65. A difference of 0.565 points with SD of 1.9 with a sample size of 480 participants would provide 90% power (SAS V 9.4 PROC POWER).

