7.2. Primary Efficacy Variable and Analysis

The primary efficacy variable for this study is the change from Baseline to Week 65 in the UHDRS-TFC. The calculation of the UHDRS-TFC is detailed in Appendix 12.1.1.

The null hypothesis represents no difference between the therapeutic efficacy response in the active treatment group compared to the placebo group:

$$H_0: \mu_A = \mu_P$$

$$H_A: \mu_A \neq \mu_P$$

Where μ_A is the mean change from Baseline to Week 65 in UHDRS-TFC for participants randomized to pridopidine (Active) and μ_P is the mean change from Baseline to Week 65 in UHDRS-TFC for participants randomized to the placebo group. Under the alternative hypothesis, there exists a difference between the therapeutic efficacy response in the pridopidine (active) group compared to the placebo group.

Based on regulatory feedback, the hypothesis testing will be based on the main estimand separately defined for EMA and non-EMA regions.

For non-EMA regions, the main estimand is defined as **non-EMA-Estimand**:

- Treatment: Pridopidine 45 mg bid or placebo (on background of standard of care) that participants are randomized to
- Population: Early HD Participants (HDI & HD2) defined through the study inclusion/exclusion criteria. The mITT population will be used in analyzing this estimand
- Variable: Change from Baseline to Week 65 in UHDRS-TFC
- Population Level Summary: LS-Mean difference between pridopidine and placebo from MMRM model in change of UHDRS-TFC from Baseline to Week 65
- ICEs and Strategies for Addressing ICEs:

Treatment policy strategy will be used to handle the ICEs, where occurrence of an ICE is irrelevant. All observed values will be used regardless of occurrence of an ICE. No imputation is performed.

Analysis will be performed on in-clinic observed data using MMRM. The model will include the following effects:-treatment, Baseline UHDRS-TFC, region (Europe, North America), neuroleptic use (yes, no), Baseline HD stage (HDI and HD2), categorical week, and treatment by categorical week interaction.

The unstructured covariance matrix for repeated observations within participants will be used. If the model does not converge, then a simpler covariance structure with fewer parameters will be used, and we will examine these structures in the following order based on the first structure below that converges:

1. Toeplitz with heterogeneity (TOEPH),
2. Autoregressive with heterogeneous (1) [ARH(1)],

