To investigate the additional covariates that may have an effect on change in NfL over time, more covariates will also be added one at a time or altogether to the above model: CAG repeats, age, sex, CAP score, BMI, region, Baseline UHDRS-TFC, Baseline cUHDRS, Baseline Q-Motor [REDACTED] Baseline UHDRS-TMS, Baseline SDMT, and Baseline SWR. When all covariates are added to the model together, a stepwise model selection approach (specifically, a variable needs to be significant at the level of 0.25 to enter the model during the first forwardstep and to be significant at the level of 0.10 to remain in during the second backwardstep) will be adopted in order to see the most influential covariates on the change in NfL over time. Each covariate will be tested at a type I error level ≤ 0.05 , two-sided and the 95% two-sided CIs of the effect estimates will be computed.

- (2) To investigate how Baseline NfL, as a covariate, impacts change from Baseline to Weeks 26, 52, 65 and 78 in efficacy endpoints including UHDRS-TFC, cUHDRS, Q-Motor [REDACTED], UHDRS-TMS, SDMT, and SWR accounting for the effect of pridopidine 45 mg bid vs placebo.

The main analysis is based on the change from Baseline in UHDRS-TFC, cUHDRS, Q-Motor [REDACTED] UHDRS-TMS, SDMT and SWR over time. Each dependent

variable will be fit by one model. Similar analyses will be repeated for actual values of the endpoints.

Analysis will be performed on observed data using MMRM separately for actual values and change from Baseline. The model will include the following effects: *treatment*, *categorical weeks*, *Baseline value of efficacy endpoint to be analyzed*, *Baseline log₂(NfL)*, randomization stratification factors (*HD stage* and *neuroleptic use at Baseline*), interaction effects of *treatment*categorical weeks*, and *treatment*Baseline log₂(NfL)*. The spatial power covariance matrix for repeated observations within participants will be used. The denominator degrees of freedom for the tests of fixed effects will be approximated by Kenward-Roger method.

Baseline log₂(NfL) and its interaction with other factors will be tested at a type I error level ≤ 0.05 , two-sided and the 95% two-sided CI of the parameters will be computed.

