The LSM and the associated SE of the Baseline NfL-adjusted efficacy endpoint at some specified Baseline NfL values (such as median, first quartile [low level], and third quartile [high level]) for each treatment group, and the LSM, 95% CI and p-value for the treatment difference (pridopidine 45 mg bid vs. placebo) will be presented for all visits.

To investigate the additional covariates that may have an effect on the efficacy endpoints, more covariates will also be added one at a time or altogether to above model: CAG repeats, age, sex, CAP score, BMI, region. When all covariates are added to the model together, a stepwise model selection approach, as described in Objective (1), will be adopted to see the most influential covariates on the change in NfL over time. Each covariate will be tested at a type I error level ≤ 0.05 , two-sided and the 95% two-sided CIs of the parameters will be computed.

(3) To investigate the relationship between change in NfL over time and change in clinical efficacy endpoints including UHDRS-TFC, cUHDRS, Q-Motor [REDACTED], UHDRS-TMS, SDMT and SWR accounting for the effect of pridopidine 45 mg bid vs placebo.

The dependent variables investigated are clinical outcomes such as UHDRS-TFC, cUHDRS, Q-Motor [REDACTED] UHDRS-TMS, SDMT and SWR over time, with one dependent variable fit at a time.

The main analysis is based on change from baseline in both efficacy endpoints and $\log_2(\text{NfL})$, and similar analyses will be repeated for actual values of efficacy endpoints and $\log_2(\text{NfL})$. Analysis will be performed on observed data using MMRM separately for actual values and change from Baseline over time. The model for change from Baseline in a specific efficacy endpoint over time will include the following effects: *treatment*, *categorical weeks*, *Baseline value of efficacy endpoint to be analyzed*, randomization stratification factors (*HD stage* and *neuroleptic use at Baseline*), *change from Baseline in log₂(NfL)*, interaction effects of *treatment*categorical weeks*, *treatment*change from Baseline in log₂(NfL)*. The spatial power covariance matrix for repeated observations within participants will be used. The denominator degrees of freedom for the tests of fixed effects will be approximated by Kenward-Roger method.

The effect of *change from Baseline in log₂(NfL)* by treatment group will be tested at a type I error level ≤ 0.05 , two-sided and the 95% two-sided CI of the parameter will be computed.

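### The NfL mixed models in SAP 9.1.2 assume one variance for all visits, with no fallback; if the spread of change grows with time, their visit-level standard errors would be too small late and too large early.

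*SAP*

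**What the plan says.** SAP 9.1.2 repeats one covariance sentence under Objectives (1), (2) and (3): "The spatial power covariance matrix for repeated observations within participants will be used". It adds "The denominator degrees of freedom for the tests of fixed effects will be approximated by Kenward-Roger method". No heterogeneous version, fallback structure or empirical (sandwich) variance is named. The models are fitted to change from Baseline and again to actual values.

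Objective (1) models log2(NfL). Objective (2) asks how Baseline NfL "impacts change from Baseline to Weeks 26, 52, 65 and 78 in efficacy endpoints". Both report LS means and a treatment difference with CI and p-value at every visit; for Objective (2) the result "for the treatment difference (pridopidine 45 mg bid vs. placebo) will be presented for all visits". In Objective (2), Baseline log2(NfL) and its interactions "will be tested at a type I error level ≤ 0.05 , two-sided".

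Elsewhere the SAP differs:

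- SAP 7.2, primary MMRM: "The unstructured covariance matrix for repeated observations within participants will be used". Of its six ordered fallbacks, the first three allow a different variance at each visit.
- SAP 7.3.2: subgroup models, including the split at median Baseline NfL, follow the primary covariance approach.
- SAP 7.4.3: extends those subgroup analyses to log2-transformed NfL.
- SAP 7.7: the open-label MMRMs refer back to SAP 7.2.

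Protocol 9.4.8 calls for MMRMs on NfL but names no covariance structure. The SAP gives no reason for the different choice in 9.1.2.

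**The concern.** Spatial power sets the covariance between two visits to sigma² × rho^distance, so the variance is sigma² at every visit. If the true variance differs by visit, the model pools it. It then understates the standard error where the spread is wide and overstates it where the spread is narrow. Kenward-Roger works from the assumed covariance model and does not repair a wrong variance pattern.

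The SAP preface says that the rate of progression can vary greatly, and Protocol 8.1.1 gives different annual TFC declines by stage. If participants decline at different rates, change from Baseline should fan out between Week 26 and Week 78. In that case the late-visit CIs and p-values in Objectives (1) and (2) would look firmer than they are.

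There is also an inconsistency that needs no assumption. The overall log2(NfL) model uses spatial power, while the subgroup analyses of log2(NfL) use the SAP 7.2 approach.

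**Working it through.** **Inputs from the documents.** Visits are at Weeks 26, 52, 65 and 78 (SAP 9.1.2). Allocation is 1:1. The only SD given is for UHDRS-TFC change at Week 65: "with an SD of 1.9 points, using a two-tailed t-test at a significance level of 0.05" (SAP 3.3).

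**The plan's own figures reproduce.** The SAP gives no figure for the NfL models, so this check covers only the SD input.

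- 372 participants, 186 per arm: SE = 1.9 × √(2/186) = 0.197; 0.7/0.197 = 3.55; power = Φ(3.55 − 1.96) = 94.4% (stated 94%).
- Dropout: 372/(1 − 0.225) = 480 (stated 480).
- 480 participants, 240 per arm: SE = 1.9 × √(2/240) = 0.173; 0.565/0.173 = 3.26; power = Φ(3.26 − 1.96) = 90.3% (stated 90%).

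**Assumptions, not in the documents.** SD(t) = 1.9 × (t/65)^k with k = 0, 0.25, 0.5, 1 and −0.25; true correlation 0.8 per 13 weeks; complete data.

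**Method.** Find the sigma and rho that maximise the expected Gaussian likelihood of a spatial power model under each assumed true covariance. With complete data, at each visit:

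- model SE / true SE = fitted SD / true SD
- actual two-sided type I error = 2 × (1 − Φ(1.96 × ratio))

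For k = 0.25 the fitted SD is 1.778. At Week 78 the true SD is 1.9 × (78/65)^0.25 = 1.989, so the ratio is 1.778/1.989 = 0.894 and the type I error is 2 × (1 − Φ(1.752)) = 8.0%.

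| Assumed SD pattern | True SD, Wk 26 / 52 / 65 / 78 | Fitted SD | Model SE / true SE | Type I error |
|---|---|---|---|---|
| Constant | 1.90 / 1.90 / 1.90 / 1.90 | 1.90 | 1.00 / 1.00 / 1.00 / 1.00 | 5% throughout |
| t^0.25 | 1.51 / 1.80 / 1.90 / 1.99 | 1.78 | 1.18 / 0.99 / 0.94 / 0.89 | 2.1 / 5.2 / 6.7 / 8.0% |
| t^0.5 | 1.20 / 1.70 / 1.90 / 2.08 | 1.71 | 1.42 / 1.00 / 0.90 / 0.82 | 0.5 / 4.9 / 7.8 / 10.8% |
| t (linear) | 0.76 / 1.52 / 1.90 / 2.28 | 1.66 | 2.19 / 1.09 / 0.87 / 0.73 | <0.1 / 3.2 / 8.7 / 15.3% |
| t^−0.25 (shrinking) | 2.39 / 2.01 / 1.90 / 1.82 | 2.09 | 0.88 / 1.04 / 1.10 / 1.15 | 8.6 / 4.1 / 3.1 / 2.4% |

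The ratios depend on the shape of the SD curve, not its level, so the TFC value of 1.9 drops out. Whether any of these shapes fits cUHDRS, TMS, SDMT, SWR, Q-Motor or log2(NfL) is unknown.

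**Robustness.**

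- Random slopes dominated by measurement noise: 1.07 / 1.02 / 0.98 / 0.95, so at most about 7%.
- Monotone dropout (22.5% by Week 65; 85% of Week 65 completers seen at Week 78, an assumption) under t^0.5: 1.38 / 0.98 / 0.88 / 0.80. With 240 per arm, spatial power reports SEs of 0.159 / 0.165 / 0.168 / 0.176. The true SEs are 0.115 / 0.168 / 0.192 / 0.219, and unstructured gives 0.115 / 0.168 / 0.191 / 0.219.
- Other correlation patterns, or adding Week 39, change the ratios little.

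**Effects of NfL itself.** The Objective (2) model contains treatment × week and treatment × Baseline log2(NfL), but no NfL × week term. The Objective (3) model has no NfL × week term either. Each NfL coefficient is therefore a single value across visits. For a covariate that is fixed over time, with power-decay correlation, model SE / true SE is 0.99-1.01 for t^0.25 to t^0.5 growth and at most 1.04 for linear growth.

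**The case against.** The strongest reply is that growth in spread is not shown. A reader might infer that the late standard errors are too small as a matter of fact. The documents do not support that: they give one SD, for one endpoint, at one visit. Constant variance gives no error and shrinking variance reverses the direction. This stands, and the point is conditional for that reason.

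A reader might also infer that tests of the NfL effects are distorted in opposite directions at early and late visits. They are not, because those effects are pooled over visits. Under random slopes the pooled SE can be too small (ratio about 0.88-0.96), but that comes from misfit of the correlation and is a separate matter. Objective (3) specifies no visit-level treatment difference, so the early/late pattern is not claimed there.

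Disagreement with the primary model is not in itself a defect. Objective (2) adds NfL terms, omits region and includes Week 78, so the results would differ under any covariance.

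Spatial power is also a recognised choice for unequally spaced visits (gaps of 26, 13 and 13 weeks). It handles spacing through the correlation, however, and does nothing for unequal variance.

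Finally, the NfL analyses are exploratory, lie outside the testing hierarchy and include stepwise selection, so no confirmatory conclusion depends on them. That limits the importance. It does not make a visit-level CI correct if the variance pattern is wrong.

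**Conclusion.** The point holds as a conditional one. SAP 9.1.2 is an unexplained outlier: a single-variance structure with no fallback, where the rest of the SAP's repeated-measures modelling follows SAP 7.2.

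If the SD of change grows at a rate between t^0.25 and linear, the visit-specific LS means and treatment differences in Objectives (1) and (2) would have SEs:

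- about 11-27% too small at Week 78 (type I error about 8-15%);
- about 6-13% too small at Week 65 (about 7-9%);
- roughly right at Week 52 (up to 9% too large under linear growth);
- about 18% or more too large at Week 26.

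These are complete-data figures; the assumed dropout makes the late-visit shortfall slightly larger. With near-constant variance the error is 0 to about 7%. Direction and size rest on the assumed SD curve. The primary and secondary analyses are not affected.

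**What to change.** In all NfL MMRMs of SAP 9.1.2, replace spatial power with the unstructured covariance and the SAP 7.2 fallback order, and keep spatial power only as the last fallback. This is valid whether the variance grows, shrinks or stays flat, and it aligns the overall log2(NfL) model with its own subgroup analyses.

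The cost is negligible. Four visits need 4 × 5/2 = 10 covariance parameters instead of 2, with about 480 participants planned. No new data are needed and no confirmatory test changes.

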Another simpler approach to perform a simple linear model on the change from Baseline of these clinical outcomes at the specified timepoint may be performed. For Week 65 analysis, the model will include the following effects: *treatment*, Baseline $\log_2(NfL)$, $\log_2(NfL)$ at Weeks 26, 52 and 65, and interaction effects of *treatment** $\log_2(NfL)$ at Baseline and Weeks 26, 52 and 65. Each covariate related to $\log_2(NfL)$ will be tested at a type I error level ≤ 0.05 , two-sided and the 95% two-sided CI of the parameters will be computed.

To investigate the additional possible covariates that can have an effect on change in efficacy endpoints over time, more covariates will also be added one at a time or altogether to the above model: CAG repeats, age, CAP score, BMI, region. When all covariates are added to the model together, a stepwise model selection approach, as described in Objective (1), will be adopted to see the most influential covariates on the change in NfL over time. Each covariate will be tested at a type I error level ≤ 0.05 , two-sided and the 95% two-sided CI of the parameters will be computed.

(4) To investigate the proportion of participants with no increase from Baseline to Weeks 26, 52, 65 and 78 in plasma NfL levels. Other thresholds may also be explored.

The dependent variable is a binary variable which is defined as follows:

$$\text{Dependent variable} = \begin{cases} 1 & \text{if Change from Baseline in } \log_2(NfL) \leq 0 \\ 0 & \text{otherwise} \end{cases}$$

This binary variable dichotomizes changes from Baseline in $\log_2(NfL)$ over time to show whether or not there is a beneficial decrease in $\log_2(NfL)$ from Baseline. Analysis will be performed on the binary data at each visit using logistic regression model. In this model, the log odds of the dependent variable are modelled.

The model will include the following fixed effects: *treatment*, Baseline $\log_2(NfL)$, randomization stratification factors (*HD stage and neuroleptic use at Baseline*), interaction effect of *treatment***Baseline log₂(NfL)*.

Each fixed effect will be tested at a type I error level ≤ 0.05 , two-sided, and the 95% two-sided confidence intervals (CI) of the parameters will be computed. Odds Ratios of treatment effect with their 95% CI at each visit will be presented in analysis.

Subgroup analysis which divides the participants by median Baseline NfL level will be performed for above objectives where applicable.

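### The main NfL Objective (3) MMRM leaves out Baseline log2(NfL), so its NfL slope may mix Baseline prognosis with the change-change association: modestly for change scores, heavily for the repeat on actual values.

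*SAP*

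**What the plan says.** SAP 9.1.2 states Objective (3) as: "To investigate the relationship between change in NfL over time and change in clinical efficacy endpoints". Its main analysis is an MMRM on change from Baseline. "The model for change from Baseline in a specific efficacy endpoint over time will include the following effects": treatment, categorical week, the Baseline value of the efficacy endpoint, HD stage, neuroleptic use, change in log2(NfL), treatment by week, and treatment by change in log2(NfL). The effect of change in log2(NfL) "by treatment group will be tested at a type I error level" of 0.05, two-sided. The section adds that "similar analyses will be repeated for actual values of efficacy endpoints" and log2(NfL), without a separate covariate list for that repeat.

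Baseline log2(NfL) appears in the models for Objectives (1), (2) and (4). Objective (2) exists "To investigate how Baseline NfL, as a covariate, impacts change from Baseline to Weeks 26, 52, 65 and 78 in efficacy endpoints". Objective (3) also has an alternative that contains Baseline log2(NfL): a "simple linear model on the change from Baseline of these clinical outcomes at the specified timepoint may be performed". A further step, "To investigate the additional possible covariates that can have an effect on change in efficacy endpoints over time", names "CAG repeats, age, CAP score, BMI, region", which does not include Baseline NfL. A subgroup split at median Baseline NfL is planned for the NfL objectives where applicable. Protocol 9.4.8 says only that treatment and other covariates will be accounted for.

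**The concern.** The SAP treats Baseline NfL as a possible predictor of decline (Objective (2)) and as a covariate for change in NfL (Objective (1)). If both links exist, Baseline NfL confounds the association that Objective (3) sets out to estimate, and the main model does not hold it fixed. A significant slope could then arise partly from where participants started and not from how their NfL moved.

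The repeat on actual values is more exposed. With Baseline efficacy in the model but Baseline NfL not, the coefficient on the current NfL level is largely the effect of the Baseline level. Someone reading it as evidence that NfL change tracks clinical change could be misled.

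**Working it through.** **Plan's own figure.** None exists for the NfL models. The primary sample size figures do reproduce (94.4% power at N=372; 90.3% at N=480 with a difference of 0.565), so N=480 and SD 1.9 for UHDRS-TFC change (SAP 3.3) are used as inputs.

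**Assumed inputs, not in the documents.** True log2(NfL) level B: between-person SD 0.6. Measurement errors e0 and et: SD 0.15 to 0.25. Independent true change d: SD 0.15. Correlation r of Baseline NfL with efficacy change: 0 to 0.3. Slope κ of true NfL change on B: −0.15, 0 or +0.15. In every case there is no change-change relationship.

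**Definitions.** Observed baseline X0 = B + e0. Observed change C = κB + et − e0 + d. Actual value N = X0 + C. Efficacy change Y = gP + residual (SD 1.9), where P is the prognostic quantity and g = −r × 1.9 / √(1−r²) / SD(P). At one visit the unadjusted slope is g × Cov(P,C)/Var(C) for change and g × Cov(P,N)/Var(N) for actual values.

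**A. True level prognostic, κ = 0.** Cov(B,C) = 0, so the unadjusted change slope is exactly 0.

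**B. Observed baseline prognostic, κ = 0; r = 0.2, error SD 0.25.**
- Var(X0) = 0.36 + 0.0625 = 0.4225, so g = −0.2 × 1.9 / √0.96 / 0.65 = −0.597. Var(Y) = 0.597² × 0.4225 + 3.61 = 3.760.
- Change: Cov = −0.0625 and Var(C) = 2 × 0.0625 + 0.0225 = 0.1475. Slope = +0.253. SE with 240 per arm = √[(3.760 − 0.253² × 0.1475)/(0.1475 × 240)] = 0.326. Rejection 0.12.
- Actual: Cov = 0.36 and Var(N) = 0.36 + 0.0625 + 0.0225 = 0.445. Slope = −0.483. SE = √[(3.760 − 0.483² × 0.445)/(0.445 × 240)] = 0.185. Rejection Φ(2.61 − 1.96) = 0.74.

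**C. True NfL change depends on a prognostic level; r = 0.3, error SD 0.15.** g = −0.3 × 1.9 / √0.91 / 0.6 = −0.996. Var(C) = 0.15² × 0.36 + 3 × 0.0225 = 0.0756. The change slope is −0.996 × (κ × 0.36)/0.0756: +0.71 for κ = −0.15 and −0.71 for κ = +0.15. The sign follows κ, which is unknown.

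**Rejection at nominal 0.05, without → with Baseline log2(NfL):**

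| Mechanism | Change, one visit | Change, MMRM | Actual, one visit | Actual, MMRM |
|---|---|---|---|---|
| Not prognostic | 0.05 → 0.05 | 0.048 → 0.045 | 0.05 → 0.05 | 0.04 → 0.04 |
| A | 0.05 → 0.12–0.21 | 0.048–0.058 → 0.055–0.082 | 0.81–0.99 → 0.12–0.21 | 0.35–0.76 → 0.03 |
| B | 0.07–0.22 → 0.05 | 0.058–0.085 → 0.042–0.068 | 0.74–0.98 → 0.05 | 0.34–0.67 → 0.04–0.06 |
| C | 0.17–0.33 → 0.07–0.11 | 0.095–0.185 → 0.055–0.090 | 0.83–0.996 → 0.07–0.11 | 0.56–0.97 → 0.03–0.06 |

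The MMRM columns are simulations: 480 participants, four visits, spatial power covariance, arm-specific slopes, z-test in place of Kenward-Roger, strata omitted. The change column used 400 runs (Monte Carlo SE about 0.011). The actual-value column used 300 runs, error SD 0.1 to 0.2 and r 0.15 to 0.25, so it is not matched cell by cell to the one-visit column. A further MMRM simulation gave 0.035–0.098 → 0.025–0.07 for change and 0.64–0.89 → 0.025–0.07 for actual values.

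**Why one fix serves both versions.** Since N = X0 + C, an arm-specific slope on N and one on C are the same coefficient once X0 and treatment by X0 are in the model. Likewise, efficacy value and efficacy change give the same slope once Baseline efficacy is included.

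**Recovery of a real relationship.** With a true slope of −2 and error SD 0.10 (one visit), the unadjusted slope was −1.06 in A, −0.83 to −0.91 in B, and −0.15 (κ = −0.15) or −2.27 (κ = +0.15) in C. Adjusted slopes ran from −1.07 to −1.31.

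**The case against.** Several points on the other side stand.

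- A reader might infer that the test picks up regression to the mean instead of the change-change relationship. That does not follow. Mechanism A shows that random measurement error alone leaves the unadjusted change slope at zero. The slope does estimate the change-change association, with possible confounding added.
- A reader might also infer that the bias has the wrong sign and masks a real relationship. Mechanism C shows the sign turning with κ, and near-masking appeared in only one extreme setting. The documents contain nothing that fixes κ.
- Adjustment is not free of risk. When the baseline is a noisy measure of a prognostic level, adding it creates some bias: 0.12–0.21 at one visit, 0.055–0.082 in the MMRM.
- The SAP does not list covariates for the actual-value repeat, so the large figures assume that the same list carries over. A level-on-level association is also a legitimate quantity. The error lies in reading it as a change-change result.
- The optional linear model contains Baseline log2(NfL), and the later add-on covariates might refer to that model. But it only may be performed and covers one time point, and a median split leaves Baseline differences within each half. These soften the gap in the main model without closing it.
- The analysis is exploratory. Nothing in the documents makes it the sole basis for a claim that NfL tracks benefit, and the treatment effect on NfL is Objective (1), which adjusts for Baseline NfL.

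**Conclusion.** The omission is plain in the text, unexplained, and inconsistent with the neighbouring objectives. If Baseline NfL is prognostic, the Objective (3) slope may mix that prognosis with the association of interest. For the change-score MMRM the effect is modest: rejection of about 0.05 to 0.19 under a true null, in a direction that the documents cannot settle. For the actual-value repeat, if it uses the same covariate list, the coefficient mainly reflects the Baseline level (0.34 to 0.97, against 0.03 to 0.06 adjusted). If Baseline NfL is not prognostic there is no problem in either version.

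All sizes rest on the assumed NfL variances, reliability and correlations. The consequence is confined to exploratory biomarker interpretation. The primary endpoint and the sequential testing in SAP 5.6 are untouched.

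**What to change.** In SAP 9.1.2, Objective (3):

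- Pre-specify the MMRM with Baseline log2(NfL) and treatment by Baseline log2(NfL) added, and report it beside the version now planned.
- State which association is targeted: change in NfL at a given Baseline level, or change regardless of Baseline level.
- List the covariates for the actual-value repeat, and interpret it as a change-change relationship only from the adjusted model.

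The cost is wording and at most two degrees of freedom, using a covariate already collected. The downside is that error in the Baseline measurement can introduce a bias through the adjustment, slight in the MMRM runs. That is the reason to report both versions; a marked disagreement between them would itself show that Baseline level matters to the result.
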